1.1. Synopsis

Please refer to the Master Protocol LDOS-21-001 for a comprehensive background and rationale for this study of a combination of famotidine and celecoxib as a post-exposure prophylaxis (PEP) for newly-infected COVID-19 patients.

This study (LDOS-21-001-02) is designed to test the efficacy and safety of combinations of two well-understood agents—famotidine and celecoxib. Each of these agents separately demonstrate clinical activity in mitigating COVID-19 disease symptoms or severity, and each of which appear to have separate and complementary mechanisms of action.

Study Description: This is a virtual Phase 2 randomized, placebo-controlled, double-blind study to evaluate the safety and efficacy of the combination of famotidine and celecoxib as a post-exposure prophylaxis (PEP) for newly-infected COVID-19 patients. Qualifying patients will have been confirmed positive for COVID-19 and have symptoms of WHO Ordinal Scale for Clinical Improvement with scores of \leq 3 on the 11–point scale (Table 2), and will be randomly assigned, in a 1: ratio, to one of two regimens, with 659 participants per group, as follows:

• **Group 1 (Study Product)**: 80 mg famotidine (PO) QID + celecoxib 400 mg first dose, followed by 200 mg (PO) BID for 5 days. Following this 5-day period, participants will continue their 80 mg famotidine QID treatment for an additional nine days.

Group 2 (Reference Comparator): Matching placebo for famotidine and celecoxib respectively, QID + BID for five days. Following this 5-day period, participants will continue to receive matching famotidine placebo, QID, for an additional 9 days.

There will be a subsequent follow-up period of 90 days from Baseline (Day 1 of treatment).

Score	Descriptor	Patient State
0	Uninfected; no viral RNA detected	Uninfected
1	Asymptomatic; viral RNA detected	Ambulatory Mild
2	Symptomatic; independent	Ambulatory Mild
3	Symptomatic; assistance needed	Ambulatory Mild
4	Hospitalized; no oxygen therapy	Hospitalized Moderate
5	Hospitalized; oxygen by mask or nasal prongs	Hospitalized Moderate
6	Hospitalized; oxygen by NIV or high flow	Hospitalized Severe
7	Intubation and mechanical ventilation, pO2/FiO2 \geq 150 or SpO2/FiO2 \geq 200	Hospitalized Severe
8	Mechanical ventilation pO2/FiO2 <150 (SpO2/FiO2 <200) or vasopressors	Hospitalized Severe
9	Mechanical ventilation, pO2/FiO2 <150 and vasopressors, dialysis, or ECMO	Hospitalized Severe

Table 2:WHO 11-point Clinical Progression Scale

Score	Descriptor	Patient State
10	Dead	Dead

Study Objectives and Endpoints: The objectives of the study are to evaluate the safety and efficacy of famotidine and celecoxib when used as a treatment for COVID-19. The study specific objectives and endpoints are described Table 3 and within Section 1.4.

Table 3:	Objectives and	l Endpoints
----------	-----------------------	-------------

Objectives	Endpoints
Primary	
Efficacy	The percentage of patients with at least one COVID-19–related medically attended contact, due to increased symptom severity, through Day 30 in both the placebo and the overall trial population, or incidence of death (all-cause mortality). Medically attended visits could include telemedicine visits, in-person physician visits, urgent care or emergency department visits, hospitalization.
Secondary	
Safety	Incidence of Related Serious Adverse Events (SAE) Incidence of discontinuation due to related SAE Oxygenation Status (oxygen saturation ≤ 94%, necessitating supplemental oxygen, as measured by daily pulse oximeter ratings)
Efficacy	The percentage of participants with at least three COVID-19–related medically attended contacts due to increased symptom severity, through Day 30.
Exploratory	
Efficacy	Rate of hospitalization, as well as all-cause mortality rate. Additionally, multiple Patient-Reported Outcome (PRO) endpoints will be used to establish how participants feel and function in relation to disease and treatment. These endpoints will include daily ratings of symptom type and severity. Symptoms will be captured using a 0-10, 11-point numerical rating scale ranging from "None" to "Extreme." Daily ratings of perceived incapacity will also be obtained using a 0-10, 11-point numerical rating scale ranging from "No Limitation" to "Extreme Limitation."
	At the conclusion of their participation, participants will also report on their global impression of therapeutic change using an established 7-pt Patient's Global Impression of Change Scale (PGIC), their belief regarding active vs. placebo group assignment, and their qualitative impressions of their illness experience elicited through narrative probes. In addition to the above subjective measures, daily body temperature ratings will be captured and recorded.

Inclusion criteria:

- 1. Participant must be at least 18 years of age, inclusive, at the time of signing the Informed Consent.
- 2. Confirmed SARS-CoV-2 PCR positive or positive by FDA-authorized at-home antigen test within 5 days of enrollment (i.e., signing the ICF), as shown by medical history and reported PCR or antigen test result; confirmatory PCR testing is required for participants with an antigen-positive test result before starting study medication.
- 3. Reports having one or more symptoms consistent with SARS-CoV-2 (as defined in Appendix 3, Table 4 of the Master Protocol, LDOS-21-001).
- 4. COVID-19 Diagnosis must be WHO Grade <3, as referenced in Section 1.1, Table 2
- 5. Contraceptive use by men or women should be consistent with **Appendix 4** of the Master Protocol (**LDOS-21-001**).
- 6. Reliable access to the Internet via a browser installed on personal device or computer.
- 7. Capable of understanding and providing of signed informed consent.

Exclusion criteria:

Participants are excluded from the study if any of the following criteria apply:

- 1. Pregnancy or breastfeeding
- 2. Ongoing antiviral or antiretroviral treatment
- 3. Known history of HIV
- Ongoing anti-inflammatory treatment that cannot be temporarily discontinued during the study. This includes nonsteroidal anti-inflammatory drugs (NSAIDs), and corticosteroids

 including Dexamethasone (dexamethasone administration restricted to recommended standard of care use per NIH COVID-19 Guidelines)
 - a. drugs dependent on gastric pH for absorption, e.g., dasatinib, delavirdine, mesylate, cefditoren, and fosamprenavir
 - b. tizanidine (CYP1A2) substrate,
 - c. drugs that interfere with hemostasis (e.g., warfarin, aspirin, selective serotonin reuptake inhibitors [SSRIs]/serotonin norepinephrine reuptake inhibitors [SNRIs]),
 - d. angiotensin converting enzyme (ACE) inhibitors, angiotensin receptor blockers (ARB), or beta-blockers,
 - e. diuretics,
 - f. digoxin.
- 5. Ongoing treatment that cannot be temporarily discontinued during the study, with: antimalarials, antiarrhythmics, tricyclic antidepressants, natalizumab, quinolones, macrolides, agalsidase alfa and beta
- 6. Ongoing famotidine, celecoxib or other COVID-19 clinical investigational treatment(s) within the past 30 days, or current participation in another investigational clinical trial.

LEAP-CT as a Post-exposure Prophylaxis for Newly-infected COVID-19 Patients

- 7. History of asthma, urticaria, or other allergic-type reactions after taking aspirin or other NSAIDs
- 8. History of immunosuppression
- 9. Rejection of participation by Principal Investigator or Sponsor
- 10. Any contraindication for famotidine or celecoxib treatment:
 - a. Famotidine or celecoxib hypersensitivity
 - b. Retinopathy, visual field or visual acuity disturbances
 - c. History of cardiovascular disease, such as congestive heart failure, QT prolongation, myocardial infarct, bradycardia (< 50 bpm), ventricular tachycardia, other arrhythmias
 - d. Myasthenia gravis
 - e. Psoriasis or porphyria
 - f. History of renal failure/dialysis or a glomerular clearance <60 mL/min
 - g. History of severe hypoglycemia
 - h. Moderate or severe hepatic impairment, e.g., Child-Pugh Class B or C
 - i. Known or suspected to be poor CYP2C9 metabolizers based on genotype or previous history or experience with other CYP2C9 substrates, such as warfarin and phenytoin.

Data Collection: Throughout the study, participants will enter data using their personal webenabled devices via a secure internet URL, into an adaptive self-reporting platform (**Determined**), and transmitted to the ClinTrial database. This will allow for tracking increases and decreases in symptom severity and capability to perform tasks throughout the treatment phase of the study and, subsequently, through the follow-up phase. Participants will be able to report their symptoms, potential adverse events (AEs), and all other required data, once daily each day. Tracking symptoms during follow-up will help establish and identify the emergence of new symptoms or return of previously noted symptoms following treatment.

Data Safety Monitoring Board: An independent Data Safety Monitoring Board (DSMB) will be established to monitor safety data at regular intervals to ensure the continuing safety of participants enrolled in the study. Summary data tables and listings, as well as any individual participant data will be provided to the DSMB by unblinded personnel (e.g., independent unblinded biostatistician), who will not be the same staff responsible for the analysis and operational aspects of the study. Summary data may be initially provided in semi-unblinded fashion (e.g., participants sorted by study treatment regimen, without disclosure of the actual treatment administered). Should the DSMB require fully-unblinded data, these tables and listings will then be provided.

Statistical Methods: The study will aim to enroll up to 1465 participants, which assumes a 10% screen failure rate, with a final allocation of 659 participants in the treatment arm and 659 in the control arm.

This sample size of ensures a power of 90% at a 2-sided α of 5%, assuming a 1:1 randomization, a placebo rate of 6% (of participants with at least one COVID-19–related medically attended contact, due to increased symptom severity, or incidence of death due to COVID-19 through Day 30) and an assumed relative risk reduction of 65% to 2.4% in the active treatment arms. The statistical test of the null hypothesis of no between-group difference in proportions, as specified

in the primary endpoint, will be tested using a χ^2 test at a two-sided 5% significance level. An interim analysis for futility will be performed after 50% of participants have completed the primary endpoint assessment at day 30. Safety analyses will be performed on the Safety Population, consisting of all participants who are randomized and received study drug, analyzed by actual treatment arm. A more detailed description of the statistical methods can be found in Section 7.

Protocol Title: A virtual Phase 2 randomized, placebo-controlled, double-blind study to evaluate the safety and efficacy of the combination of famotidine and celecoxib as a post-exposure prophylaxis (PEP) for newly-infected COVID-19 patients.

Short Title: LEAP-CT as a post-exposure prophylaxis for newly-infected COVID-19 patients.

Rationale: Please refer to the Master Protocol LDOS-21-001 for a comprehensive background and rationale for this study of a combination of famotidine and celecoxib as post-exposure prophylaxis (PEP) for newly-infected COVID-19 patients.

Overall Design: This is a Phase 2, randomized double-blind placebo-controlled decentralized virtual study in which outpatient participants, newly diagnosed for COVID-19, will be randomized in a 1:1 ratio to one of two study groups (1 treatment group and 1 control group). The study is designed as a virtual trial in that it will be conducted, *in situ*, with home-based participants entering self-assessments via a web-enabled adaptive platform – The participants will be under the oversight of regionally based investigators who will be responsible for study conduct and the review of blinded data on a periodic basis.

Intervention Groups and Duration: The treatment regimen for this study is shown in Table 4.

Regimen	Dose	# of Participants
Group 1	80 mg famotidine (PO) QID + celecoxib 400 mg first dose, followed by 200 mg (PO) BID for 5 days. Following this 5-day period, participants will continue their 80 mg famotidine QID treatment for an additional nine days.	659
Group 2	Matching Placebo for famotidine and celecoxib respectively – QID + BID for five days. Following this 5-day period, participants will continue to receive matching famotidine Placebo, QID, for an additional 9 days.	659

Table 4:Study Interventions

Disclosure Statement: This is a Phase 2 randomized, double-blind, placebo-controlled study to evaluate the safety and efficacy of the combination of famotidine and celecoxib as a post-exposure prophylaxis (PEP) for newly-infected for COVID-19 patients. These participants will not be hospitalized at enrollment, and all study activities will be performed at the participant's home. Investigational product and matching Placebo will be shipped directly to the participant from the Sponsor's supplier. There will be no other physical location where participants are seen. Virtual research teams will be organized by U.S. geographical region under the oversight of a Principal Investigator licensed to practice in the state(s) in which participants reside. Each site or group of affiliated sites will be required to designate at least one physical location to serve as a research facility for storage of any paper documents generated, mail correspondence or location

for inspection activity. This designated location will be listed as a research facility under Section #3 of Form FDA 1572.

Number of Participants: Approximately 1800 participants will be screened to achieve 1465 randomly assigned to study intervention and at least 1318 evaluable participants for an estimated total of 659 evaluable participants per group.

Study Design: The study design is shown schematically in Figure 1.

Schedule of Assessments: The participants will have responsibility for entering self-assessment of symptom severity, body temperature, blood oxygen concentration (spO2) using Sponsor-supplied devices, using the web-based platform. The study Schedule of Assessments is shown in Table 5.

LEAP-CT as a Post-exposure Prophylaxis for Newly-infected COVID-19 Patients

Version 2.0; 11 April 2022

Table 5:Schedule of Assessments

Study Activities and Assessments	Screening & Randomization ¹		Treatment	Period		Observ	ation Period ²
Visit Number ³	1	2	3	4	5	6	7
Study Day		Day 1 Baseline/ Start of Treatment ⁴	Day 7(±1)	Day 14 (±1)	Day 30(±1) End of Treatment	Day 60	Day 90
Informed consent ⁵	Х						
Inclusion and Exclusion criteria	Х	Х					
Demographics	Х						
Medical History, including weight reporting ⁶	X						
Concomitant medication review	X	X	X	X	Х		
Blood draw for comprehensive metabolic panel (mobile phlebotomy & laboratory service)	Х		X	X			
Nasal swab for confirmatory PCR test for at-home antigen positive test prescreened participants (mobile phlebotomy & laboratory service)	X						
Randomization and initiation of drug shipment ⁷	Х						
Review of reported baseline symptoms		Х		X			
Confirmation of Study Drug Receipt & Initial Dose		X					
Confirmation of Study Drug Return Shipment ⁸					Х		
Review of eDiary for study drug compliance ⁹			X	X	Х		
Adverse Events Review		X	X	X	Х		
Participant Intake of study drug		Daily on Day	s 1–14				

Study Activities and Assessments	Screening & Randomization ¹		Treatment Po	eriod		Observati	on Period ²
Visit Number ³	1	2	3	4	5	6	7
Study Day		Day 1 Baseline/ Start of Treatment ⁴	Day 7(±1)	Day 14 (±1)	Day 30(±1) End of Treatment	Day 60	Day 90
Symptom questionnaires, spO2, and temperature		Daily for the entire treatment and observation period (Days 1–90)					
Mobile ECG		Х	Х	Х			

¹ Participant will complete demography, medical history, concomitant medications, and questions regarding inclusion and exclusion criteria [including results of SARS-CoV-2 PCR test and self-administered urine pregnancy test] via Site will review participant responses and confirm information with participant by Visit 2.

² During the observational period, while participant is not taking any IP, participant will record long term symptoms for Covid-19, but will be directed to consult with his/her primary care physician (PCP) for follow up of any health changes. Planned contacts with participants on Days 60 and 90 will be performed by study support staff only to confirm continued participation in the study.

³All participant visit activities will be performed remotely.

⁴ Visit 1/participant informed consent must be performed within 5 days of a positive PCR or at-home antigen test, as per inclusion criteria. As IP will be shipped to the participant upon randomization, treatment start date (Visit 2/Day 1) may not occur until a few days after initiation of IP shipment. Participant will start treatment after IP receipt and review of inclusion/exclusion criteria with site. Date of first IP intake will always be considered Day 1, even if IP shipment is delayed outside of expected timeframe. If IP intake is delayed due to shipment, this will not be considered a protocol deviation.

⁵ Participant will complete Informed Consent Process via

⁶ Medical history should include relevant history from within the past 3 years, with inclusion of relevant medical events within the past 5 years.

⁷ IP will be shipped directly from drug depot to participants after randomization occurs within 2.

⁸ Participant will be provided return envelope for return of IP directly from participant to drug depot. At Visit 4, site will confirm with participant that he/she has shipped the IP back to the depot. Depot will be responsible for performing IP accountability.

⁹ Participant eDiary review will be performed by the clinical site staff.

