1.4.2. Endpoints

Primary efficacy endpoint will include the percentage of participants with at least one COVID-19–related medically attended contact, due to increased symptom severity, through Day 30 in both the placebo and the investigational treatment population, or incidence of death (all-cause mortality). Medically-attended visits could include telemedicine visits, in-person physician visits, urgent care or emergency department visits, hospitalization.

Secondary endpoints will include the incidence of related serious adverse events (SAEs) and the incidence of discontinuation due to related SAEs, as well as oxygenation status (oxygen saturation \leq 94%, necessitating supplemental oxygen as measured by daily pulse oximeter ratings).

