3.9. Dose Modification

Dose modification from the specified study regimens will be required if any of the following occur after the administration of study drugs:

- a participant's glomerular clearance (GFR) drops to <60 mL/min without developing QT prolongation or CNS AEs (i.e., delirium, hallucinations, disorientation, or seizures) after the results from their weekly laboratory results have been obtained by the investigator; or
- a QT wave prolongation is registered on their mobile ECG monitor; or
- a central nervous system (CNS) AE (i.e., delirium, hallucinations, disorientation, or seizures) is reported by the subject.

If any of the above occur, then the investigator will instruct the participant to stop all scheduled study medications.

For those participants with a drop in GFR and no QT prolongation or CNS AEs, they may resume study medications after testing demonstrates the GFR is >60 mL/min. Upon resolution, study drugs can be added back in stepwise fashion, e.g., BID, then TID, and finally QID. All missed or withheld doses will be noted in

For participants that had a QT prolongation or CNS AE (i.e., delirium, hallucinations, disorientation, or seizures), study medication will be permanently stopped and they will be followed for safety for the remainder of their study participation (Day 90).

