5.7. Adverse Events and Serious Adverse Events

The definitions of an AE or SAE can be found in **Appendix 2** of the Master Protocol (**LDOS-21-001**). CNS-related AEs including confusion, delirium, hallucinations, disorientation, agitation, seizures, and lethargy will be captured in the eCRF as an AE of special interest (AESI).

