7.4.2. Efficacy Analyses

The **primary efficacy** endpoint, the percentage of patients with at least one COVID-19–related medically attended contact, due to increased symptom severity or death (all-cause mortality) through Day 30, will be analyzed using a two group χ^2 test with pooled variances and no continuity correction. Statistics and the associated 95% confidence interval will be provided. The primary efficacy analysis will be performed using the ITT and will be repeated for robustness purposes with the PP.

In case of missing data of the primary endpoint at day 30 (Visit 4), the primary analysis will consider participants (with missing primary endpoint data until day 30) as having at least one medically attended visit. For sensitivity purposes, the primary efficacy analysis will be repeated by excluding participants with missing primary endpoint until day 30 (Complete Case Analysis).

The **secondary safety endpoints**: Incidence of Related Serious Adverse Events (SAE), Incidence of discontinuation due to related SAE and Incidence of death will also be analyzed using a χ^2 test. Descriptive statistics including exploratory confidence intervals/p-values will be provided.

All **other efficacy endpoints** will be analyzed in an exploratory manner by applying appropriate statistical methods (e.g. χ^2 test for incidences, log rank test and Kaplan Meier method for cumulative incidences, ANOVA for continuous variables) using the FAS set. Descriptive statistics including exploratory confidence intervals/p-values will be delivered.

All **other safety related endpoints** will be analyzed in a descriptive way by providing descriptive statistics and/or shift tables from baseline to the assessment visits.

For more details of the statistical analysis, methods/models refer to the SAP.

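### A drug stop mandated by Section 3.9 reaches a named between-arm safety comparison only if the event is both serious and judged related

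*Protocol*

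**What the plan says.** Table 3 in the Synopsis lists three secondary safety endpoints: related SAEs, "Incidence of discontinuation due to related SAE", and oxygen saturation at or below 94% "necessitating supplemental oxygen, as measured by daily pulse oximeter ratings". Section 1.4.2 repeats them as "the incidence of related serious adverse events (SAEs) and the incidence of discontinuation due to related SAEs, as well as oxygenation status". Section 7.4.2 assigns a chi-square test to related SAEs and then adds: "Incidence of discontinuation due to related SAE and Incidence of death will also be analyzed". Death is thus included there and oxygenation is not. The same section calls the resulting confidence intervals and p-values exploratory. All remaining safety endpoints get descriptive statistics and/or shift tables.

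Section 3.9 names three triggers: GFR below 60 mL/min without a QT or CNS event, QT prolongation registered on the mobile ECG, and a reported CNS event (delirium, hallucinations, disorientation or seizures). It then states: "If any of the above occur, then the investigator will instruct the participant to stop all scheduled study medications". Participants stopped for GFR alone may resume later. Those stopped for QT or CNS events may not. Section 5.7 makes CNS events adverse events of special interest in the eCRF.

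**The concern.** Section 3.9 and the monitoring that supports it (metabolic panels and mobile ECGs at Days 7 and 14) show which drug risks the sponsor takes seriously. The discontinuation endpoint adds two filters, seriousness and relatedness, that the stopping rule does not use. A participant taken off drug permanently for QT prolongation that is not classed as an SAE has no event in the endpoint that carries the word discontinuation.

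The SAE endpoint has the relatedness filter too. In a double-blind placebo-controlled trial the comparison of arms already separates drug effect from background illness, so case-by-case attribution is not needed for the main count. It also brings in judgement that may differ between investigators.

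Safety is a stated objective, and Table 6 concedes that data on the combination at these doses are limited. The named endpoints could look alike in the two arms while the protocol's own stopping rules operated unequally.

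**Working it through.** **Step 1: set the conditions side by side.**

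| Event | Section 3.9 action | Enters a named secondary safety endpoint? |
|---|---|---|
| GFR below 60, no QT or CNS event | Stop all drug; may resume | Only if a related SAE; whether a temporary stop is a discontinuation is not stated |
| QT prolongation on mobile ECG | Stop permanently | Only if a related SAE |
| Listed CNS event | Stop permanently | Only if a related SAE; otherwise recorded as an event of special interest |

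Oxygenation status and death do not count drug stops, so they do not fill the gap. This step rests on the text alone.

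**Step 2: illustrate the size.** The protocol states no rate for these stops, so there is no figure of its own to reproduce. From Section 7.2 I take 659 per arm in the Full Analysis population. By Table 8 that population has the same entry condition as the Safety population (randomised, at least one dose). The stop rates and the fraction *f* of stops that are both serious and related are assumptions.

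Expected count per arm = 659 × stop rate × *f*. For 3% versus 1%:
- All stops (*f* = 1): 659 × 0.03 = 19.8 versus 659 × 0.01 = 6.6.
- *f* = 0.05: 1.0 versus 0.3.
- *f* = 0.20: 4.0 versus 1.3.

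Approximate power at two-sided 5% is Φ[(d − 1.96·se0)/se1], where d is the difference in proportions, se0 the pooled and se1 the unpooled standard error. For 3% versus 1% with all stops counted:
- se0 = √(0.02 × 0.98 × 2/659) = 0.00771
- se1 = √((0.03 × 0.97 + 0.01 × 0.99)/659) = 0.00769
- power = Φ[(0.02 − 0.01512)/0.00769] = Φ(0.63) = 0.74

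| Assumed stop rates | All stops, expected | Power, all stops | Counted at *f* = 0.05 | Counted at *f* = 0.20 | Power, *f* = 0.05 to 0.20 |
|---|---|---|---|---|---|
| 2% v 0.5% | 13.2 v 3.3 | 0.69 | 0.7 v 0.2 | 2.6 v 0.7 | 0.08 to 0.19 |
| 3% v 1% | 19.8 v 6.6 | 0.74 | 1.0 v 0.3 | 4.0 v 1.3 | 0.08 to 0.21 |
| 5% v 2% | 33.0 v 13.2 | 0.84 | 1.6 v 0.7 | 6.6 v 2.6 | 0.10 to 0.26 |

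The normal approximation is rough at counts this small, so the low powers only show an order of magnitude.

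**Step 3: the same contrast as observed data.** With 20 versus 7 stops, the uncorrected chi-square is 1318 × (20 × 652 − 7 × 639)² / (27 × 1291 × 659²) = 6.39, p = 0.011. With 33 versus 13 it is 9.01, p = 0.003. In the limiting case where no stop is a related SAE, the current endpoint reads 0 versus 0. The upper 95% bound for 0/659 is then 1 − 0.05^(1/659) = 0.45% one-sided, or 1 − 0.025^(1/659) = 0.56% as the upper end of a two-sided interval.

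**The case against.** The strongest reply is that nothing is lost. CNS events are recorded as events of special interest, AEs are reviewed at Days 1, 7, 14 and 30, panels and ECGs are scheduled, withheld doses are noted, and the DSMB receives safety tables by regimen. Tables of AEs by action taken are ordinary SAP content, and that plan is not shown. The secondary safety p-values are exploratory and Section 7.1 has no safety hypothesis, so naming these stops would add no confirmatory test.

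Much of this stands. A reader might infer that mandated stops go uncounted altogether, or that SAEs are the only safety outcomes compared. The documents do not support either: the stops can be described, and oxygenation and death are listed. Nor do COVID-19 events simply vanish under the relatedness filter. COVID-19-related hospitalisations due to worsening symptoms and all-cause deaths are in the primary endpoint, and hospitalisation and mortality rates are exploratory endpoints.

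It is also tempting to say that these stops are usually non-serious. That is an assumption: the SAE definition is in the Master Protocol, which is not shown. It is plausible for an isolated laboratory or ECG finding and weaker for seizures or delirium.

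The objection does not remove the definition itself. It is stated in three places, and an SAP that followed it exactly would still leave a non-serious or unrelated mandated stop outside every named safety endpoint.

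**Conclusion.** The point holds as a weakness in how the endpoints are defined. It is neither an arithmetical error nor a fault in the stopping rules. Besides oxygenation and death, the named endpoints capture a Section 3.9 stop only when the event is a related SAE. Any other such stop is at most described.

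That conclusion follows from the text and needs no assumed rate. Its practical size is unknown. The illustration suggests that most stops would fall outside the endpoint if few are serious and related: 80 to 95% when *f* is 0.20 to 0.05. Both the stop rates and *f* are assumed, and the 0 versus 0 case depends entirely on assuming that no stop is a related SAE. Because the comparisons are exploratory, what is at stake is how clearly the trial reports tolerability, not its error rate. The change is worth making because it is cheap and safety is a stated objective.

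**What to change.** In Table 3, Section 1.4.2 and Section 7.4.2, define:

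1. Incidence of any SAE regardless of relatedness, with related SAEs as a subset.
2. Incidence of permanent study-drug discontinuation due to any AE or any Section 3.9 trigger, shown by trigger (GFR, QT, CNS), with discontinuation due to a related SAE as a subset. Report temporary interruptions separately, such as GFR stops later resumed, so that they are not mixed with permanent stops.

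Compare arms in the Safety population with the same exploratory chi-square and confidence intervals. Keep oxygenation status and death as they are.

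The cost is endpoint wording and a few table shells. AE review, metabolic panels, ECGs and the record of withheld doses already supply the data, and no stopping rule, dose or procedure changes. One small downside is that SAEs from COVID-19 itself add background events to the any-SAE count in both arms, which is why the related subset is retained.

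### The only secondary efficacy endpoint in Table 3, three or more contacts by Day 30, has no death component, so death before a third contact counts as a non-event

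*Protocol*

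**What the plan says.** Table 3 in the Synopsis (Section 1.1) has a single entry under secondary efficacy: "The percentage of participants with at least three" COVID-19-related "medically attended contacts due to increased symptom severity, through Day 30". The definition ends there.

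The primary entry in the same table needs only one such contact and adds a death clause, "or incidence of death (all-cause mortality". It also lists what may count as a contact: "Medically attended visits could include telemedicine visits, in-person physician visits, urgent care or emergency department visits, hospitalization".

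Death and admission appear elsewhere too. Table 3 places "Rate of hospitalization, as well as all-cause mortality rate" under exploratory efficacy, and Section 7.4.2 names incidence of death among the secondary safety endpoints to be compared by chi-square test.

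Section 7.4.2 gives one imputation rule. It applies to the primary endpoint and treats participants with missing data "as having at least one medically attended visit". All efficacy endpoints other than the primary are to be analysed in an exploratory way on the full analysis set, and no rule for deaths is given for them.

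Section 1.4.2 does not mention the three-contact endpoint among the secondary endpoints. It lists related serious adverse events, discontinuation due to them, and oxygenation status.

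**The concern.** Death stops the accumulation of contacts. If an endpoint counts contacts and does not make death an event, the earlier a participant dies, the less likely that participant is to be counted. The primary endpoint avoids this by making death an event. The secondary endpoint does not, although it has the same Day 30 window and the same kind of contact.

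The resulting order is at odds with the protocol's own severity scale. Table 2 puts death at 10 and hospitalized states at 4 to 9, above every ambulatory state (1 to 3). On the three-contact endpoint, a death or a lone admission can fall in the non-event group while three telemedicine calls fall in the event group.

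What is at stake is how one secondary result is read. A between-arm difference in early deaths would lower the event count in the arm with more deaths, so the comparison could not be interpreted without the mortality data beside it.

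**Working it through.** The protocol states no rate, power or sample size for this endpoint, so there is no figure of its own to reproduce. The check is a reading of the definition, followed by a note on scale.

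**1. Scoring typical courses.** Under the written definition a participant is a secondary event if the number of qualifying contacts by Day 30 is at least 3. A participant is a primary event if that number is at least 1, or if death occurs. The table assumes that all contacts are COVID-19-related and due to worsening, and that one admission counts as one contact. The second assumption is needed because the protocol gives no counting rule.

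| Course to Day 30 | Contacts | Primary | Three-contact endpoint |
|---|---|---|---|
| Death, no contact | 0 | event | non-event |
| Death after one or two contacts | 1 or 2 | event | non-event |
| One admission, no other contact | 1 | event | non-event |
| One admission and one other contact | 2 | event | non-event |
| One admission and two other contacts | 3 | event | event |
| Three telemedicine calls | 3 | event | event |

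The first two rows do not depend on how an admission is counted. The third and fourth do. If an emergency visit leading to admission were counted as two contacts, some admitted participants would move to event.

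**2. Does another section repair it?** The imputation rule in Section 7.4.2 is written for the primary endpoint. Even if it were carried over, it assigns at least one visit, which does not establish three. If deaths were instead handled as missing and dropped, they would still not be events.

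**3. Scale.** Section 7.2 assumes primary event rates of 6% on placebo and 2.4% on active treatment, with 659 per group.

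- Placebo: 0.06 × 659 = 39.5 expected primary events.
- Active: 0.024 × 659 = 15.8 expected primary events.

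The share of these participants who would reach three contacts is not given. Taking 10%, 20% and 30% as pure assumptions, with the same relative effect:

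| Assumed share | Placebo events | Active events |
|---|---|---|
| 10% | 39.54 × 0.1 = 4.0 | 15.816 × 0.1 = 1.6 |
| 20% | 39.54 × 0.2 = 7.9 | 15.816 × 0.2 = 3.2 |
| 30% | 39.54 × 0.3 = 11.9 | 15.816 × 0.3 = 4.7 |

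Over this range the endpoint rests on few events, so each death scored one way or the other is a visible part of the count. This does not measure the distortion, because the number of deaths before a third contact is unknown.

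**The case against.** The strongest case against is that little depends on this endpoint. Death from any cause and COVID-19-related admission are both primary events. Hospitalization and mortality are reported as exploratory outcomes, and death is also tested among the secondary safety endpoints. The hypotheses in Section 7.1 concern the primary parameter only. The three-contact endpoint can also be read simply as a measure of repeated healthcare use, and counting rules are often left to the statistical analysis plan, which is not shown. All of this stands, and it limits the weight of the point. It does not remove it: what counts as an event is part of the endpoint definition, and the protocol has fixed that definition without death.

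A reader might infer more, but the documents do not support it:

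- **That hospitalization is left out.** It is a listed contact type and counts toward the three. An admitted participant with two other contacts by Day 30 is an event.
- **That a death or admission is scored as a success, or that the endpoint was meant to capture greater severity than the primary.** The protocol defines no success category and states no purpose for the endpoint. Section 3.8.1 applies the term clinical failure to participants hospitalized for worsening or needing oxygen whose study medication is stopped before dexamethasone, though it ties that label to no endpoint.
- **That an effective treatment would look harmful.** This would require averted deaths or admissions to turn into courses with three contacts, and nothing in the protocol says they would.
- **That a stated share of severe outcomes is missed.** No death, admission or three-contact rate is given.

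**Conclusion.** The point holds in a limited form. The only secondary efficacy endpoint in Table 3 has no death component, so death before a third contact is a non-event, unlike in the primary endpoint, while three telemedicine calls are an event. A single admission with fewer than two other contacts by Day 30 is also a non-event, provided an admission counts as one contact.

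The defect affects the interpretation of one endpoint that is analysed in an exploratory manner. The primary analysis, its error rate and its power are untouched, and no death or COVID-19 admission goes unreported. Its numerical size cannot be derived from the protocol. A scoring rule in the unseen statistical analysis plan could mitigate it, but the protocol definition as it stands does not.

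**What to change.** Keep the three-contact definition and its Day 30 window, and make death from any cause through Day 30 an alternative qualifying event, as in the primary endpoint. Table 3, Section 1.4.2 and Section 7.4.2 give the primary's death component as all-cause, whereas the statistical part of the Synopsis and Section 7.1 speak of death due to COVID-19. The two endpoints should use the same definition once that is settled.

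Add a supportive analysis in which COVID-19 hospitalization also counts as an event. This belongs in a supportive analysis because making any admission a stand-alone event is more of a design choice than a repair. State whether an emergency visit that leads to admission is one contact or two. Report the contact count alone as a utilisation summary. List the endpoint in Section 1.4.2 so that its status agrees with Table 3.

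The cost is a change of wording. The data are already needed for the primary and exploratory endpoints, and no visits or participants are added. The downside is that the endpoint becomes a composite, so its components should be shown separately.
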